CAMCI: Advancing the Use of Computerized Screening in Healthcare

Clinical Trial:NCT03512301Secondary ID:NIH: 2SB1AG037357-04A1DATE:Approved by DSMB – July 18, 2019
Uploaded to clinicaltrials.gov - February 14, 2025

Analysis Plan

Validation of CAMCI Algorithm and MoCA with Neuropsychological Adjudication

CAMCI will group participants into three classifications: impaired, non-impaired, and intermediate. Likewise, the neuropsychological adjudication will provide a consensus classification for participants into impaired, non-impaired, and intermediate and thus, CAMCI classifications will be compared to clinical adjudication. Similarly, MoCA classification will be evaluated against the neuropsychological adjudication. MoCA scores are classified as non-impaired (MoCA \geq 26) or impaired (MoCA <17), with intermediate scores occurring between 18-25. To validate the CAMCI and MoCA against the neuropsychological adjudication, we will evaluate positive and negative predictive agreement, accuracy and error bias. Accuracy is defined as the correct identification using CAMCI: ACC=[TP+TN]/total; error bias will be a contrast ratio of false positives and false negatives: FP-FN/FP+FN.

Agreement analysis

Two methods will be used to evaluate the agreement of CAMCI to non-reference (Montreal Cognitive Assessment, MoCA) and reference (clinical adjudication) standards. First, using linear regression, agreement analysis will be done to compare the subject device, CAMCI score (expected to range from 0-50), and the MoCA score (ranging from 0-30). Agreement will be evaluated using the scatterplot, linear regression equation and confidence intervals, and Pearson correlation. It will be expected that each of these evaluation methods will show that those patients who score high on the CAMCI will also score high on the MoCA, indicating agreement between the range of scores that are non-impaired. Likewise, we will expect to see low scores on the CAMCI to be found in those who also show low MoCA scores, indicating agreement in the ranges of impaired scores on both assessments.

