Next, agreement will be assessed using the clinical adjudication categories and the CAMCI classifications. The following table will be used to display the frequencies showing the distribution of patients into the CAMCI classifications (impaired, non-impaired, intermediate/indeterminate) by clinical adjudication (normal, impaired, indeterminate). From this summary, percent agreement (positive and negative), confidence interval estimates, and quadratic weighted kappa will be used to assess the agreement between CAMCI and the reference standard. Finally, this analysis will be repeated with the omission of the intermediate group to show the performance of CAMCI for those who are clearly impaired and clearly non-impaired.

Classification						
TEST		Impaired	Intermediate	Non-impaired		
	Impaired	TP*	FP	FP		
	Intermediate	FN	TP	FP		
	Non-impaired	FN	FN	TN		

Example, Agreement analysis (general case in 3x3):

* TP=True Positive, TN=True Negative, FP=False Positive, FN=False Negative

Example, Agreement analysis (for current study):

Classification by Clinical Adjudication							
CAMCI		Impaired	Intermediate	Non-impaired			
	Impaired	а	b	С			
	Intermediate	d	е	f			
	Non-impaired	g	h	i			

Classification by Clinical Adjudication							
МоСА		Impaired	Intermediate	Non-impaired			
	Impaired	а	b	С			
	Intermediate	d	е	f			
	Non-impaired	g	h	i			

Positive percent agreement (PPA, %) = 100 X (a + e) / (a + b + c + e + f) Negative percent agreement (NPA, %) = 100 X (i) / (d + g + h + i) Accuracy (ACC) = [(a + e) + (i)] / total n Error Symmetry ([(b + c + f) – (d + g + h)] / total n

Change Metric

Test-retest descriptive statistics (mean, standard deviation) will be calculated and compared for the clinical groups (impaired, intermediate, non-impaired). Difference scores will be calculated and analyzed for retest effect and to identify any patterns (improvement/decline) that might differ between the groups on retest. Finally, repeated measures analyses will be used to assess group X retest differences. This information will be used to determine whether adjustments will be made to the reliable change calculations.

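### The SAP puts true/false positive/negative labels on a three-by-three table without defining a positive screen, and the labels fit no single definition, so FP, FN, PPA, NPA and error bias cannot be read as screening errors

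*SAP*

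**What the plan says.** Under the SAP heading on validation of the CAMCI algorithm and MoCA, "CAMCI will group participants into three classifications: impaired, non-impaired, and intermediate", and "the neuropsychological adjudication will provide a consensus classification for participants into impaired, non-impaired, and intermediate". The same section defines accuracy as (TP+TN)/total and says that "error bias will be a contrast ratio of false positives and false negatives", with denominator FP+FN.

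The SAP's Agreement analysis section gives a key for the 3x3 table, with the test in rows and the adjudicated class in columns. Its footnote reads "TP=True Positive, TN=True Negative, FP=False Positive, FN=False Negative". The test-intermediate row is labelled "Intermediate FN TP FP". With the SAP's cell letters, the whole key is:

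| Test \ Adjudication | Impaired | Intermediate | Non-impaired |
|---|---|---|---|
| Impaired | a = TP | b = FP | c = FP |
| Intermediate | d = FN | e = TP | f = FP |
| Non-impaired | g = FN | h = FN | i = TN |

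The formulas follow: "Positive percent agreement (PPA, %) = 100 X (a + e) / (a + b + c + e + f"), "Negative percent agreement (NPA, %) = 100 X (i) / (d + g + h + i"), and "Accuracy (ACC) = [(a + e) + (i)] / total n Error Symmetry ([(b + c + f) – (d + g + h)] / total n". The same layout is printed for CAMCI and for MoCA. Quadratic weighted kappa and a repeat analysis omitting the intermediate group are also planned.

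**The concern.** TP, FP, FN and TN have meaning only once the classes that count as positive are fixed for the test and for the reference. The SAP does not fix them, and its labels imply different choices in different cells.

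A reader will take an FN as a missed case and an FP as a false alarm. In the SAP's FN total, an impaired person whom CAMCI places in the intermediate class (d) counts the same as one whom it calls non-impaired (g). In its FP total, an adjudicated-intermediate person called impaired (b) counts the same as a non-impaired person called impaired (c).

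This matters because the protocol (section 4.12) gives the project's goal as commercialising CAMCI as a quick screen, and Specific Aim 1 seeks FDA agreement on a regulatory plan. Misses and false alarms are central to such a claim.

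**Working it through.** **Step 1: do the formulas follow the key?** Yes. Under the key TP = a+e, FP = b+c+f, FN = d+g+h and TN = i.
- The PPA denominator a+b+c+e+f equals TP+FP.
- The NPA denominator d+g+h+i equals TN+FN.
- ACC is (TP+TN)/n.
- Error Symmetry is (FP-FN)/n.

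The labels are therefore what the SAP intends to use, not a damaged table. Error Symmetry and the earlier error bias share a numerator, and so a sign. Their denominators differ (n against FP+FN).

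**Step 2: does any definition of positive give this key?** No. Along the test-intermediate row, FN in d makes the result negative, while TP in e and FP in f make it positive. Down the adjudicated-intermediate column, FP in b makes the reference negative, while TP in e and FN in h make it positive. Each contradiction alone rules out every binary split. Enumerating all 8 x 8 = 64 splits of test and reference confirms it. The natural candidates fail as follows:

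| Positive on test | Positive on reference | Cells that disagree with the key |
|---|---|---|
| Impaired or intermediate | Impaired or intermediate | b, d (should be TP) |
| Impaired only | Impaired only | e, f, h (should be TN) |
| Impaired only | Impaired or intermediate | b, e, f |
| Impaired or intermediate | Impaired only | d, e, h |

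**Step 3: effect on error direction.** The SAP numerator is (b+c+f) - (d+g+h).
- With impaired or intermediate as positive, FP-FN = (c+f) - (g+h). The SAP adds (b-d).
- With impaired only as positive, FP-FN = (b+c) - (d+g). The SAP adds (f-h).

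The sign reverses relative to a cut when the added term opposes that cut's difference and is larger in size.

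**Step 4: illustration.** The documents give no cell counts, so these are assumed. The total of 420 is the Protocol 1 enrolment (protocol section 3.2). The table a to i = 36, 14, 4, 40, 106, 34, 4, 20, 162 has column totals of 80 impaired, 140 intermediate and 200 non-impaired.

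| Definition | FP | FN | Error bias (FP-FN)/(FP+FN) | (FP-FN)/420 |
|---|---|---|---|---|
| SAP key | 14+4+34 = 52 | 40+4+20 = 64 | -12/116 = -0.10 | -0.029 |
| Impaired or intermediate positive | 4+34 = 38 | 4+20 = 24 | +14/62 = +0.23 | +0.033 |
| Impaired only positive | 14+4 = 18 | 40+4 = 44 | -26/62 = -0.42 | -0.062 |

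The added terms account for the gaps: 14 + (14-40) = -12, and -26 + (34-20) = -12.

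NPA moves too. It is 162/226 = 72% under the key. In the same form (TN over all test negatives) with impaired or intermediate as positive, it is 162/(162+24) = 162/186 = 87%.

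**Step 5: a second assumed table.** With a to i = 60, 20, 5, 40, 80, 40, 5, 10, 160 (n = 420), Error Symmetry is (65-55)/420 = +0.024 under the SAP. It is (45-15)/420 = +0.071 with impaired or intermediate as positive, and (25-45)/420 = -0.048 with impaired only. Here the SAP agrees in sign with the first cut and disagrees with the second. No particular reversal is forced.

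**The case against.** The strongest reply is that the key is a coherent ordinal rule. Cells above the diagonal are over-calls and cells below it are under-calls, so Error Symmetry has the right sign for net over-call against under-call. This stands. The fault lies in giving the cells binary screening names and building PPA, NPA and error bias on them.

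A reader might infer that counting d as a miss is simply an error, or that the SAP will report the wrong direction. The documents support neither:
- If only impaired is positive, d is properly an FN. The SAP cannot rest on that reading, because it labels e as TP and f as FP. But it never says that an intermediate CAMCI result is a positive screen, and it also calls that class indeterminate.
- In the first assumed table, the SAP's sign agrees with the impaired-only cut and differs at the other. The answer depends on the cut. That table also puts more impaired people in d (40) than in a (36), which favours a reversal.

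The plan also limits the harm. All nine frequencies are shown, so any cut can be recomputed. Quadratic weighted kappa penalises g (two steps) four times as heavily as d (one step). The repeat analysis leaves a clean 2x2 (a, c, g, i) if intermediates are dropped from both test and reference. However, the SAP does not say which are dropped, and if only adjudicated intermediates go, d remains an FN. None of these measures corrects FP, FN, PPA, NPA or error bias.

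Finally, the SAP attaches no test or acceptance threshold to these measures; they are descriptive. That bears on the weight of the point, not on its truth.

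**Conclusion.** The point holds in this form. The labels contradict each other on the face of the SAP, and that finding needs no assumption. FP, FN, PPA, NPA, error bias and Error Symmetry mix severity-grading disagreements (b, d) with misses and false alarms, for CAMCI and MoCA alike, and should not be reported as screening errors. Exact agreement (a+e+i)/n and weighted kappa are sound as they are. The former is three-class agreement, not binary accuracy.

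The size is illustrative only. On one assumed table, error bias runs from -0.42 through the SAP's -0.10 to +0.23 according to what counts as positive. Without cell counts, a change of sign is possible but not shown to occur. Such a change would mean disagreement with a stated cut, not that the over-call/under-call index is wrong.

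**What to change.** Keep the nine-cell table, exact agreement (a+e+i)/n and quadratic weighted kappa. Rename b+c+f as over-calls and d+g+h as under-calls, and present Error Symmetry as the net of the two.

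Compute FP, FN, percent agreement and error bias from a consistent 2x2 table at each of two stated cuts:
1. Impaired or intermediate against non-impaired: TP = a+b+d+e, FP = c+f, FN = g+h, TN = i.
2. Impaired against the rest: TP = a, FP = b+c, FN = d+g, TN = e+f+h+i.

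Show b and d separately as severity-grading disagreements. Apply the same scheme to MoCA. State whether the repeat analysis drops intermediates by test, by adjudication or by both.

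The cost is a change of SAP wording and two extra 2x2 tables per instrument from the same data. The small downside is two sets of error figures instead of one.

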Change in test scores will be modelled using a Reliable Change Index (RCI) method to determine whether the change in test scores is due to the reliability of the measure (rather than due to chance alone). This method is beneficial because it is well-documented and is one that accounts for measurement error and practice effect (Chelune et al., 1993; Hensel, 2007). It has also been shown (Hsu et al., 1999) to account for regression to the mean. Reliable change will be evaluated at the 6-month, one-year, and two-year intervals.

Using normative data from a prior sample, and data gathered from the non-impaired clinical group, an appropriate strategy will be identified for the identification of cut-off scores for clinically significant change (Jacobson and Truax, 1991). Data will then be used to derive standard error of the mean (SEm), test-retest reliability coefficients, and standard error of the difference (SEdiff) statistics. The latter, SEdiff, will identify the variability in the distribution of the change scores that would be expected if there were no change between test and retest. Finally, 90% and 95% confidence intervals will be calculated to identify the amount of difference that would have to be observed in either direction to assume that the difference occurred beyond chance (at significance levels of 5% and 2.5%, respectively).

Reliable change will be calculated using the following formula for all data regardless of clinical group:

$$RC = \frac{x_2 - x_1}{SE_{diff}}$$

Using established methods (Chelune et al. 1993), index scores will classify patterns of change as "gain", "no change", and "loss". Likewise, the same individuals will be grouped based on change in clinical adjudication between those identified as impaired, intermediate, and non-impaired at each assessment, categorizing status change as "improved", "no change", and "declined". These groups will be analyzed based on the confidence intervals, accuracy, and reliable change index. Analysis will include the assessment of practice effect.

References

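### The SAP decides whether to adjust the reliable-change calculation from a group-by-retest comparison that cannot tell practice from true decline, and it does not state the form of the adjustment

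*SAP*

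**What the plan says.** The Change Metric section of the SAP first summarises test and retest scores, "compared for the clinical groups (impaired, intermediate, non-impaired". Difference scores are then "analyzed for retest effect and to identify any patterns (improvement/decline) that might differ between the groups on retest". On whether the reliable-change calculation is to be altered, the plan is: "repeated measures analyses will be used to assess group X retest differences. This information will be used to determine whether adjustments will be made". The section gives no significance level, no rule linking a result to an adjustment, and no form of adjustment. It does not limit this step to participants whose status was stable.

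The same section sets the time frame: "Reliable change will be evaluated at the 6-month, one-year, and two-year intervals". It describes the reliable change method as one that accounts for measurement error and practice. The printed formula, however, is the raw difference x2 − x1 divided by SEdiff, with no practice term, and the SAP states: "Reliable change will be calculated using the following formula for all data regardless of clinical group". Prior normative data and the non-impaired group are to be used in choosing the cut-off strategy. Practice is to be assessed, but the SAP does not say how.

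**The concern.** A correction to a reliable-change score should take out the retest artefact, that is, the change expected in someone whose true status has not moved. The SAP defines SEdiff against that same reference: it "will identify the variability in the distribution of the change scores that would be expected if there were no change between test and retest". The decision to adjust rests on something else. Over 6 to 24 months, mean change in impaired and intermediate participants is practice plus any true decline. The hypothesis tested is equal total change across groups, not equal practice. It can be rejected when practice is the same everywhere and impaired people simply get worse, which is what the metric is meant to detect.

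The change metric is part of Specific Aim 3, and its 'gain', 'no change' and 'loss' calls are to be set against change in adjudicated status. How practice is handled moves those calls materially. The decision should not hang on a comparison that confounds practice with decline, with the form of correction left open until the data have been seen.

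**Working it through.** The SAP gives no power, sample size or significance level for this step, so there is no planned figure to reproduce. Two related figures agree: 90% and 95% limits leave 5% and 2.5% per tail, and 280 + 140 = 420 in the follow-up table.

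**Inputs from the documents.** Planned retests are 280 at 6 months, 420 at 12 months and 140 at 24 months (protocol 4.11). The 90% limits give z = 1.645. The printed formula is (x2 − x1)/SEdiff.

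**Assumptions (the documents give none).** Impaired/intermediate/non-impaired mix 15/25/60%; practice 0.3 SEdiff in every group; alpha 0.05 for the interaction; normal change scores with SD of 1 SEdiff in each group; no dropout.

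**Step 1: what the test sees.** With two time points, the group-by-retest test is a one-way F test on change scores. Mean change in a group is practice minus decline, and only that difference enters.
- Practice 0.3 in all groups, decline 0.3/0.15/0: mean changes 0/0.15/0.3.
- Practice 0/0.15/0.3, no decline: mean changes 0/0.15/0.3.

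The two cases give the same distribution of the test statistic, so no sample size separates them.

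**Step 2: how often decline alone makes it significant.** The noncentrality is λ = N × [Σ w d² − (Σ w d)²], where w is group share and d is decline.
- Decline 0.5/0.25/0: Σ w d = 0.15 × 0.5 + 0.25 × 0.25 = 0.1375. Σ w d² = 0.15 × 0.25 + 0.25 × 0.0625 = 0.0531. The bracket is 0.0531 − 0.0189 = 0.0342. So λ = 4.79, 9.58 and 14.37 at N = 140, 280 and 420, and rejection is 48%, 79% and 93%. A simulation of 3,000 runs gave 50%, 79% and 94%.
- Decline 0.3/0.15/0: the bracket is 0.0342 × 0.36 = 0.0123. Rejection is 20%, 36% and 52%.
- Mixes from 10/20/70 to 25/25/50, N = 140: 16–24% for the smaller decline and 39–58% for the larger.
- No decline, equal practice: 5%.

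**Step 3: what each form of adjustment does.** Let A be the amount subtracted. With decline 0.5/0.25/0, mean change is 0.3 − 0.5 = −0.2 in impaired and 0.3 in non-impaired participants. The pooled mean is 0.3 − 0.1375 = 0.1625.

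Impaired 'loss' = Φ(−1.645 − (−0.2 − A)). Stable non-impaired false 'gain' = 1 − Φ(1.645 − (0.3 − A)).

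| Adjustment | A | Impaired 'loss' | Non-impaired false 'gain' |
|---|---|---|---|
| None (printed formula) | 0 | Φ(−1.445) = 7.4% | 1 − Φ(1.345) = 8.9% |
| Non-impaired mean | 0.3 | Φ(−1.145) = 12.6% | 5.0% |
| Pooled mean | 0.1625 | Φ(−1.2825) = 10.0% | 1 − Φ(1.5075) = 6.6% |
| Own-group mean | −0.2 impaired; 0.3 non-impaired | Φ(−1.645) = 5.0% | 5.0% |

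**Step 4: other effect sizes.** With decline 1/0.5/0 SEdiff, impaired 'loss' in the same row order is 17.2%, 26.0%, 17.9% and 5.0%. False 'gain' is 8.9% unadjusted and 8.5% pooled. In score SD units, take reliability 0.8 (SEdiff = √(2 × 0.2) = 0.632 SD), practice 0.2 SD, impaired decline 0.5 SD and mix 20/30/50%. 'Loss' is then 12.1%, 19.6%, 12.9% and 5.0%.

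**The case against.** The strongest reply is that the SAP never says a significant interaction leads to an adjustment. The phrase 'this information' also covers the descriptive statistics and the difference scores, and it only informs whether to adjust. That stands. The rates in Step 2 are the power of an assumed test under assumed effects, not the rate at which the plan would adjust.

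A reader might infer that the plan's adjustment strips real decline out of impaired participants' scores. The documents do not support that. Only own-group subtraction does so fully, and the SAP does not propose it. One formula for all clinical groups, and the use of non-impaired data for cut-offs, point away from it without ruling it out. If the non-impaired mean were subtracted, decline would be kept and detected more often than with the printed formula.

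A reader might also infer that a pooled correction does harm. Against the printed formula it does not: in Step 3 it is better on both columns, and at the larger decline slightly better (17.9% against 17.2% 'loss', 8.5% against 8.9% false 'gain'). Its shortfall is that it corrects practice only partly.

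Finally, checking whether practice differs by group is a legitimate aim. That also stands, and the fix keeps it as a sensitivity analysis. What the reply does not answer is that the stated comparison cannot serve that aim, because graded practice and graded decline look identical to it.

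**Conclusion.** The point holds in this form: the comparison that informs the adjustment measures total change, and neither the criterion nor the form of the adjustment is stated. This is more than missing detail, because the SAP says its method accounts for practice while the printed formula does not.

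Under equal practice and a moderate decline, the comparison is significant in roughly half of trials at 24 months and in more than nine in ten at 12 months. For the same decline, the undefined form of adjustment moves the impaired 'loss' rate between 5.0% and 12.6%. With no adjustment, false 'gain' in stable non-impaired participants is 8.9% instead of 5%.

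The confounding is a matter of logic and needs no assumption. The percentages rest on the assumed mix, practice, decline, alpha and absence of dropout. It should be corrected; it does not invalidate the change analysis.

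**What to change.** Replace the decision sentence in the Change Metric section with wording such as: 'For each retest interval, one practice constant will be estimated as mean change in participants adjudicated non-impaired at both test and retest, and checked against the prior normative sample if that sample has retest data. Reliable change will be ((x2 − x1) − practice)/SEdiff for all participants. Group-by-retest differences will not be used to decide on the adjustment and will be reported as evidence that CAMCI change separates the clinical groups. Differential practice will be examined as a sensitivity analysis in participants whose adjudicated class is unchanged, noting that within-class decline may remain.'

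The change needs SAP wording only, since adjudicated status at each assessment is already part of the plan. The documents do not say whether data collection is complete, and the fix does not depend on it.

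Costs:
- The practice estimate is less precise. At 24 months, at most 60% of 140 = 84 people would contribute under the assumed mix, so its standard error is about 1/√84 = 0.11 SEdiff, against 1/√140 = 0.08 with everyone.
- If stable impaired people gain less from practice, subtracting the non-impaired constant raises their false 'loss'. If they gain none it is Φ(−1.645 + 0.3) = 8.9% instead of 5%. The sensitivity analysis should show this.
- Adjudication at retest rests on a repeated paper-pencil battery and may itself carry practice effects.

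### The SAP says its reliable-change method accounts for regression to the mean, but the formula it gives does not; its stated error rates hold only on average over baseline scores

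*SAP*

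**What the plan says.** All of this is in the SAP, Change Metric.

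- The Reliable Change Index method is justified partly on the ground that it has been shown "to account for regression to the mean".
- One formula follows, RC = (x2 - x1)/SEdiff, introduced by "Reliable change will be calculated using the following formula for all data regardless of clinical group".
- SEdiff "will identify the variability in the distribution of the change scores that would be expected if there were no change between test and retest". It is to be derived from the data along with "test-retest reliability coefficients, and standard error of the difference (SEdiff) statistics"; no value of the reliability is given.
- For the cut-offs, "90% and 95% confidence intervals will be calculated to identify the amount of difference that would have to be observed in either direction", with the error rates stated as "at significance levels of 5% and 2.5%, respectively".
- Each person is then labelled gain, no change or loss, and these labels are set against change in adjudicated status.
- Earlier in the section, repeated-measures analyses of clinical group by retest are to inform whether the calculation is adjusted. No form of adjustment is given, and baseline score is not mentioned.

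**The concern.** The formula takes a person's expected retest score to be the baseline score itself. Reliability enters only through the denominator, which scales the change; nothing moves the expected retest score towards the mean according to where the person started. An index that adjusted for regression to the mean would be uncorrelated with baseline in people who have not changed. This one is not.

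The labels are applied to individuals, so an error rate that is right only on average can be wrong for the person being labelled. If the SAP's sentence is carried into the description of the metric, users will be told that a known artefact has been removed when it has not. The comparison of index change with adjudicated change would carry the same baseline-dependent misclassification.

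**Working it through.** **Inputs.** From the SAP: the formula, the 90% and 95% bands, and the 5% and 2.5% rates. Assumed, because the documents give no figures: bivariate normal scores, equal SD at both visits (set to 1), no true change, no practice effect, SEdiff = sqrt(2(1-r)), and r between 0.7 and 0.9.

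**Step 1: reproduce the stated rates.** The two-sided cut-offs are 1.645 (90%) and 1.960 (95%), which leave 5.0% and 2.5% in each tail. A simulation of 4 million stable people under the SAP formula with the 90% band gives 5.0% gain and 5.0% loss overall for r = 0.7, 0.8 and 0.9. The stated rates are therefore right as averages.

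**Step 2: correlation with baseline.** Cov(x2 - x1, x1) = r - 1 and SD(x2 - x1) = sqrt(2(1-r)), so the correlation is -(1-r)/sqrt(2(1-r)) = -sqrt((1-r)/2). For r = 0.7, 0.8 and 0.9 this is -0.39, -0.32 and -0.22. It is zero only at r = 1.

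**Step 3: error rates given baseline.** For a baseline of z SD from the population mean, the change has mean -(1-r)z and SD sqrt(1-r^2). The 90% cut-off is 1.645 × sqrt(2(1-r)). For r = 0.8 and z = -2, the mean is 0.4, the SD 0.6 and the cut-off 1.040:

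- P(gain) = 1 - Phi((1.040 - 0.4)/0.6) = 14.3%
- P(loss) = Phi((-1.040 - 0.4)/0.6) = 0.8%

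| r | z = -2: false gain | z = -2: false loss | z = -1: false gain | z = -1: false loss |
|---|---|---|---|---|
| 0.7 | 17.3% | 0.4% | 8.6% | 1.4% |
| 0.8 | 14.3% | 0.8% | 8.1% | 1.9% |
| 0.9 | 11.0% | 1.6% | 7.2% | 2.8% |

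At +1 and +2 SD, gain and loss swap. With the 95% band at z = -2, false gain is 9.9%, 8.1% and 6.0% against the stated 2.5%.

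**Step 4: several clinical groups.** The SAP expects three groups, and people regress towards the mean of their own group. An illustrative mixture was simulated with group means 0, -1 and -2 SD, shares 50%, 30% and 20%, r = 0.8 within each group, and the 90% band:

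| Subset | False gain | False loss |
|---|---|---|
| Lowest 10% of observed baselines | 10.4% | 1.7% |
| Highest 10% of observed baselines | 1.3% | 11.4% |
| Each clinical group as a whole | 5.0% | 5.0% |

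The distortion lies at the extremes of observed score and cancels within each group.

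**Step 5: would a regression-based index cure it?** Take (x2 - r x1)/sqrt(1-r^2), centred on the reference mean. In a single population the simulation gives about 5% per tail in every baseline band. Now suppose the mean, SD and r come from the non-impaired group and the index is applied to a stable impaired group centred at -2 SD. Its mean there is -2 × sqrt((1-r)/(1+r)). For r = 0.8 that is -0.667, so false loss is Phi(-1.645 + 0.667) = 16.4% and false gain 1.0%. False loss is 21.0% at r = 0.7 and 11.8% at r = 0.9. The simple RC gives 5% per tail in that group.

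**The case against.** The strongest reply is that a low observed score is not a low true level. For any fixed true score with constant error variance, x2 - x1 has mean zero, and a stable impaired group is called gain and loss at 5% each. This stands. A reader might infer from the -2 SD figures that impaired and intermediate participants as a group will be over-called as gains, or that well-functioning people as such will be over-called as losses. The documents do not support either: the SAP describes three groups, and Step 4 shows each group balanced. The figures apply to people whose observed baseline is extreme for their own population.

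A second reply is that the SAP leaves adjustments open and the metric is still being developed. That makes it too strong to say that miscalls will occur in the final metric. It does not rescue the sentence about regression to the mean: the open adjustment is to be decided from group-by-retest differences, and those would look clean while the extremes were distorted.

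A third is that practice effects complicate the picture. They do. The formula has no practice term either. With an assumed practice gain of 0.2 SD and r = 0.8, false loss at +2 SD falls from 14.3% to 8.1%, while false gain at -2 SD rises to 23.2%. Practice masks part of one side and worsens the other.

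It might also be inferred that a false loss leads to clinical work-up. No section says so, and Protocol Section 4.6 states that CAMCI scores will not be released or discussed in this study.

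**Conclusion.** The point holds in a limited form. The SAP attributes to its method a property that its only formula lacks, for any reliability below 1. The 5% and 2.5% rates are averages over baseline, not rates that apply at each baseline.

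The direction of the error does not depend on r, but the size does, and the documents give no r. Under the single-population assumptions, a -2 SD baseline gives 11.0% to 17.3% false gain and 0.4% to 1.6% false loss with the 90% band, mirrored at +2 SD. In the illustrative mixture, the lowest tenth of scorers has about 10% false gains and the highest tenth about 11% false losses. The mixture's means, shares and reliability are assumed.

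It would go too far to conclude that the cited source is wrong. It was not available to check, and its title in the SAP's reference list refers to five methods, so what it shows need not concern this formula.

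**What to change.** 1. Delete the statement on regression to the mean as applied to this formula.
2. State that the 5% and 2.5% rates are averages over baseline scores.
3. Report gain and loss rates by baseline-score band, overall and within clinical group.
4. Optionally, as a sensitivity analysis beside the simple RC, report a regression-based index: (x2 - predicted x2)/standard error of prediction, with predicted x2 = M2 + r(SD2/SD1)(x1 - M1) and standard error SD2 × sqrt(1-r^2). The M2 term also carries the mean practice effect. If M, SD and r come from the non-impaired group, either restrict interpretation to that group or state that in a stable impaired group the index over-calls loss (about 12% to 21% for a group mean of -2 SD and r from 0.9 to 0.7). It should not be the single replacement for everyone.

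The cost is a few extra tables, a less favourable description of the metric and, if step 4 is taken up, a second index to explain. No new data are needed.
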